- 2. Presence of a preexisting significant GI condition that does not have a presumed causal relationship with MPA

- 3. Evidence of any GI disorder induced by an infection, underlying medical condition, or concomitant medication other than MPA
- 4. eGFR<35 ml/min at time of possible conversion
- 5. Proteinuria >1 gram/day at time of possible conversion
- 6. Profound bone marrow suppression at the time of possible conversion as defined as:
 - Hemoglobin <10 g/dL
 - WBC <3 K/cumm
 - Platelets <100 K/cumm
- 7. Wound healing issues at time of possible conversion (eg, wound dehiscence, wound infection, incisional hernia, lymphocele, seroma)
- 8. Elevated total cholesterol (>350 mg/dL) and/or triglycerides (>500 ng/dL) at time of possible conversion
- 9. Hypersensitivity to everolimus, sirolimus, or other rapamycin deriviatives

Investigational and reference therapy:

Investigational therapy

- Everolimus tablets 0.25 mg, 0.5 mg, and/or 0.75 mg

Study design: Patients will be selected if they experience non-infectious GI adverse effects within the first 12 months post transplant. Following selection they will have a baseline screening and enrollment with a complete medical history, medication history, vital signs and labs (including tacrolimus and everolimus levels). In addition, their adverse effects and GSRS and GIQLI will be recorded. After enrollment they will have medication history, vitals, labs (including tacrolimus), and GSRS/GIQLI and adverse events recorded at months 1, 3, 6, 9, and 12 (excepting GSRS and GIQLI at month 9).

Efficacy assessments:

- Change in GSRS from baseline to month 3
- Change in GSRS subscores from baseline to month 3
- Changes in GSRS from basline to month 6 and 12
- Change in GIQLI from baseline to month 3
- Change in GIQLI subscores from baseline to month 3
- Changes in GIQLI from baseline to month 6 and 12

Other assessments:

- BPAR rates during study (compared with historical control)
- eGFR by MDRD4 from baseline to month 12 (compared to historical control)
- Death (compared with historical control)
- Graft loss (compared with historical control)

Data analysis:

Data for primary and secondary efficacy will be compared using a paired T-test.

Background

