Management of GI adverse effects following kidney transplantation has been established as a consistent challenge for transplant centers. Reduction of MPA immunosuppression may lead to adverse outcomes such as rejection or graft failure, and use of AZA has been associated with higher rates of graft loss. Everolimus has been studied in kidney transplant recipients, and has been shown to lead to similar rates of rejection and graft function compared to MPA. Thus, we have proposed this single-arm study to assess improvement in GI adverse effects in renal transplant recipients. If EVR demonstrates a significant benefit with regard to GI adverse effects while maintaining appropriate rejection prophylaxis, it may offer transplant a new option for patients who are experiencing such adverse effects while on MPA therapy.

We will assess patients within the first year post-transplant for signs and symptoms of GI adverse effects, and following ruling out infectious causes, they will be consented and converted to EVR at an initial dose of 1 mg PO BID, which will then be titrated to target trough goals between 3 - 8 ng/mL. Prior to drug initiation, patients will complete the GSRS and GIQLI surveys to assess for intensity of symptoms and associated quality of life. Patients will remain on study therapy for at least 12 months and GSRS and GIQLI will be repeated at 30 days, 3 months, 6 months, and 12 months.

These timelines were chosen to allow enough time to demonstrate a significant change in GSRS scores following conversion to EVR. We have chosen not to include an active control due to the added cost and time that would be required to enroll and follow the additional numbers needed. We will compare data on graft rejection, graft function, graft survival, and patient survival to an historic cohort of patients who were converted to AZA for GI adverse effects. They will be compared on a 2:1 basis to a group of randomly selected patients previously converted to AZA.

Objectives

Primary objectives

To determine if a switch from MMF or EC-MPS to Zortress (everolimus) due to GI intolerance results in improvement of GI symptoms, as measured with the GSRS survey.

Secondary objectives

To determine whether it is safe to switch from MMF or EC-MPS to Zortress (everolimus) due to GI intolerance from MMF/EC-MPS within 12 months post-renal transplantation.

[figure not shown]
Study design

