- 2. Adult kidney transplant recipients at Washington University/Barnes-Jewish Hospital
- 3. Experiencing GI toxicity from MPA as determined by the treating physician within 12 months postrenal transplant
- 4. On standard immunosuppression with tacrolimus and prednisone

Exclusion criteria

1. Dual organ or kidney after another solid organ transplant

2. Presence of a preexisting significant GI condition that does not have a presumed causal relationship with MPA

3. Evidence of any GI disorder induced by an infection, underlying medical condition, or concomitant medication other than MPA

- 4. eGFR<35 ml/min at time of possible conversion
- 5. Proteinuria >1 gram/day at time of possible conversion
- 6. Profound bone marrow suppression at the time of possible conversion as defined as:
 - Hemoglobin <10 g/dL
 - WBC <3 K/cumm
 - Platelets <100 K/cumm

7. Wound healing issues at time of possible conversion (eg, wound dehiscence, wound infection, incisional hernia, lymphocele, seroma)

8. Elevated total cholesterol (>350 mg/dL) and/or triglycerides (>500 ng/dL) at time of possible conversion

9. Hypersensitivity to everolimus, sirolimus, or other rapamycin deriviatives

Treatment

Investigational and control drugs

Patients enrolled in the trial will receive everolimus tablets at a starting dose of 1 mg PO BID, which will be dispensed in 0.5 mg tablets in blister-packages of 60-each.

Treatment arms

This will be a single-arm study. All patients enrolled with be assigned to the everolimus arm. We will include an observational retrospective analysis of those on AZA-based immunosuppression for comparison of risk of acute rejection, chronic rejection, graft-loss, and death, but these patients have already been allocated treatment and completed follow-up.

Treatment assignment

This will be a single-arm study. All patients enrolled with be assigned to the everolimus arm.

Treatment blinding

This will be an open-label study. All participants including researchers, subjects, and analysts will be aware of treatment allocation.

Treating the patient

Patient numbering

Patients will be numbered sequentially from 1 through 30 based on the order they complete consent and enrol in the study

Dispensing the study drug

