For all suspected rejection episodes, regardless of initiation of anti-rejection treatment, an allograft biopsy must be performed within 48 hrs. Biopsies will be read by the pathologist according to the updated Banff 2009 criteria. The results of the biopsy read by the pathologist will be recorded in the research database. The results will be used for subject management for acute rejection. The local pathologist will remain blinded to treatment. Any biopsies performed according to local practice (e.g. not for cause) should also be recorded.

Graft Loss

The allograft will be presumed to be lost on the day the subject starts dialysis and is not able to subsequently be removed from dialysis. If the subject undergoes allograft nephrectomy prior to starting permanent dialysis, then the day of nephrectomy is the day of graft loss.

Death

In the event of subject death, the SAE leading to Death should be reported to the sponsor DS&E within 24 hr.

Renal Function

Renal function by calculated eGFR using the MDRD4 formula (Coresh, 2003) from enrollment to Month 12 is a primary variable for assessment of renal function in this study. This will also be the primary method of assessment of renal function with respect to other renal endpoints.

Physical examination

A thorough physical assessment will be performed at Screening, Months 3, 6 and 12. Information about the physical examination will be recorded in the visit history document. Significant findings that are present prior to the start of the study must be included.

Vital signs

Vital signs (radial pulse rate and blood pressure) will be recorded at each study visit in the visit history document. Blood pressure and pulse rate will be assessed at the same arm each time of determination and after the subject has rested in the sitting position (may be supine if during hospitalization) for at least five minutes. Systolic and diastolic blood pressure will be measured three times using an automated validated device, e.g. OMRON, with an appropriately sized cuff. The repeat sitting measurements will be made at 1-2 minute intervals and the mean of the three measurements will be recorded on the Vital Signs CRF. In case the cuff sizes available are not large enough for the subject's arm circumference, a sphygmomanometer with an appropriately sized cuff may be used.

Height and weight

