Efficacy (secondary)

We will conduct analysis of GIQLI scores at visit 2, 3, 4, and 6 compared with baseline assessment, as well as inter-visit comparisons. Additionally, we will conduct subscore analyses of the GSRS and GIQLI at each of these timepoints. The pre-specified domains of the GSRS to be analyzed will be the abdominal pain, diarrhea and reflux scores. The GIQLI subscores will be analyzed for all domains.

Safety

Safety variables to be assessed include BPAR, graft loss, death, graft function at each study visit, discontinuation from study, discontinuation from treatment, infection, SAE, notable events, laboratory tests, and vital signs. All safety analyses will be done on the safety set. Selected variables will be analyzed using all available data including data assessed.

Health-related Quality of Life

As above.

Sample size calculation

The sample size was calculated based on the myTIME study. Sample size calculation showed that a minimum sample size of 25 patients will be required to provided 80% power to detect a change from baseline of 12 points in the total GSRS score (15-105 scale) considering a 0.05 significance level and a standard deviation of 18 and allowing for a 20% dropout. A paired t test will be utilized to compare the overall GSRS score, the GSRS subscale scores, and the GIQLI from baseline.

- Assuming a 5% 1-year rate of acute rejection, we plan to evaluate 60 historical control patients to compare differences in the secondary endpoints of acute rejection, graft survival, patient survival, and infections. The historical control group will be randomly selected from a consecutive list of patients who received a renal transplant during the same study period and were maintained on MMF 500mg-1gram BID or EC-MPS 360-720mg BID, tacrolimus, and prednisone and met stated inclusion and exclusion criteria as listed below. 30 conversion patients will be enrolled and compared 1:2 with historical controls.
- Statistical analysis for the historical control comparison will utilize the Chi-squared test for events, ANOVA for renal function outcome differences and other continuous variables, and Kaplan-Meier estimates for patient and graft survival

Ethical considerations

Regulatory and ethical compliance

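### eGFR is compared with unmatched historical controls by plain ANOVA, with no baseline adjustment and no statement of whether month-12 values or changes are analysed

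*Combined protocol and SAP*

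**What the plan says.** The analysis method appears in one bullet at the end of the Sample size calculation section (10.6): "ANOVA for renal function outcome differences and other continuous variables". No covariate is named there. I found no mention elsewhere of ANCOVA, a regression model, matching, stratification or a propensity score.

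The endpoint is described in three places, none of which defines the analysed variable:

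- Synopsis, Other assessments: "eGFR by MDRD4 from baseline to month 12 (compared to historical control".
- Renal Function, under Safety: eGFR "from enrollment to Month 12 is a primary variable for assessment of renal function in this study".
- Safety, under Analysis of secondary objectives: "graft function at each study visit".

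The controls are described in two ways. Purpose and rationale says: "They will be compared on a 2:1 basis to a group of randomly selected patients previously converted to AZA". The Sample size calculation section says: "The historical control group will be randomly selected from a consecutive list of patients who received a renal transplant during the same study period", and goes on to describe patients kept on MMF or EC-MPS with tacrolimus and prednisone. Treatment arms confirms that the comparison is retrospective: "these patients have already been allocated treatment and completed follow-up". The planned sizes are 30 and 60: "30 conversion patients will be enrolled and compared 1:2 with historical controls". The only entry restriction on renal function is the exclusion of eGFR below 35 ml/min.

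**The concern.** Drawing controls at random from a list of past patients is not random allocation. It makes the controls representative of that list, but does not make them resemble the everolimus patients. The eGFR floor removes the lowest values and leaves the rest of the distribution free to differ. If the controls are patients who stayed on MPA, they also differ in kind from patients selected because they could not tolerate it.

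Baseline eGFR usually predicts later eGFR strongly, so a pre-existing gap carries forward. Analysing month-12 values keeps most of that gap. Analysing change removes it but leaves regression to the mean, which acts in the other direction. Either could be reported as a drug effect.

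Purpose and rationale hopes that everolimus will protect graft function better than azathioprine or MPA, and this comparison would be the evidence. Leaving the variable undefined until the data are in hand also leaves open a choice that can move the estimate either way.

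**Working it through.** **Plan's own figure.** There is none for eGFR: no SD, detectable difference or power is given. The only powered analysis is the paired GSRS comparison. Its figure of 25 reproduces (20 evaluable by the two-sided paired t-test, 20/0.8 = 25) and does not bear on this point.

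**Inputs from the protocol.** Groups of 30 and 60; ANOVA; no covariate.

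**Assumptions, not in the documents.** Common eGFR SD *s* = 15 to 20 mL/min; baseline to month-12 correlation *r* = 0.5 to 0.8; illustrative baseline imbalance *D* = 5 mL/min; no true effect.

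**Formulas.** Let SE0 = *s* × √(1/30 + 1/60) = *s* × 0.2236, which is 3.35 for *s* = 15 and 4.47 for *s* = 20.

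- ANOVA of month-12 values: SE = SE0; expected spurious difference = *r* × *D*.
- ANOVA of change: SE = SE0 × √(2(1 − *r*)); expected spurious difference = (*r* − 1) × *D*.
- ANCOVA: SE = SE0 × √(1 − *r*²); expected spurious difference = 0 if the linear model holds and baseline eGFR is the only confounder.
- False-positive rate = P(|Z + difference/SE| > 1.96).

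Example, month-12 values, *s* = 15, *r* = 0.8: difference 0.8 × 5 = 4.0; 4.0/3.35 = 1.19; rate 22.2%.

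| SD | r | Month-12: SE, difference, rate | Change: SE, difference, rate | ANCOVA SE |
|---|---|---|---|---|
| 15 | 0.5 | 3.35, +2.5, 11.6% | 3.35, −2.5, 11.6% | 2.90 |
| 15 | 0.7 | 3.35, +3.5, 18.1% | 2.60, −1.5, 8.9% | 2.40 |
| 15 | 0.8 | 3.35, +4.0, 22.2% | 2.12, −1.0, 7.6% | 2.01 |
| 20 | 0.5 | 4.47, +2.5, 8.6% | 4.47, −2.5, 8.6% | 3.87 |
| 20 | 0.7 | 4.47, +3.5, 12.3% | 3.46, −1.5, 7.2% | 3.19 |
| 20 | 0.8 | 4.47, +4.0, 14.5% | 2.83, −1.0, 6.4% | 2.68 |

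**Precision.** Against month-12 ANOVA, the ANCOVA SE ratio √(1 − *r*²) runs from 0.87 to 0.60, so the SE is 13-40% smaller and the ANOVA variance is 1.33 to 2.78 times as large. Against change-score ANOVA, the ratio √((1 + *r*)/2) runs from 0.87 to 0.95, so the SE is 5-13% smaller and the variance ratio is 1.11 to 1.33. At *s* = 15 and *r* = 0.7, the difference detectable with 80% power is 9.4 mL/min (month-12 values), 7.3 (change) and 6.7 (ANCOVA). With the 24 everolimus completers that the protocol expects, these become 10.1, 7.9 and 7.2.

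**Cost to ANCOVA of the imbalance.** With *D* = 5, the variance inflation 1 + *D*²/(88 × *s*² × 0.05) is 1.025 for *s* = 15 and 1.014 for *s* = 20, which is small beside the gains.

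**The case against.** The strongest reply is that both descriptions of the endpoint, running from baseline or enrolment to month 12, suggest change from baseline, and ANOVA can be applied to change. This largely stands. A reader might infer that the plan analyses raw month-12 values and so carries the baseline gap straight into the result. The documents do not settle that, and the larger figures belong to that reading alone. On the change reading the problem is smaller but still present.

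A reader might also infer that leaving baseline out is always worse than either alternative. It is not: at a correlation of 0.5, month-12 and change-score ANOVA have the same SE and the same absolute bias of 2.5 mL/min.

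A third reply is that ANCOVA is not clearly the right model for non-randomised groups. This is fair. If the groups differ by a stable 5 mL/min that would persist without any drug effect, change from baseline is unbiased and ANCOVA is off by (1 − *r*) × 5, or 1 to 2.5 mL/min. The documents cannot show which assumption holds, and that is the reason to report both.

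Finally, the comparison is secondary and unpowered. The stated reason for 60 controls lists rejection, graft and patient survival, and infections, but not eGFR. Applying the entry criteria to controls limits imbalance somewhat, and no figure in the documents points to a gap of 5 mL/min. These points lower the priority; they do not supply a defined variable or a baseline adjustment.

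**Conclusion.** The concern holds in a bounded form. The eGFR comparison uses plain ANOVA against retrospective, unmatched controls, without baseline adjustment and without defining the analysed variable. Under the stated assumptions a 5 mL/min imbalance yields a false-positive rate of about 9-22% if month-12 values are analysed and about 6-12% if change is analysed, with spurious differences of opposite sign. ANCOVA would shorten the SE by 13-40% or 5-13% respectively. The SD, correlation and imbalance are all assumed, so these figures show the scale of the problem and do not predict the result.

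A reader might infer that ANCOVA would make the comparison unconfounded. It would not: it handles baseline eGFR only. Selection for GI toxicity, time since transplant, donor type and calendar period remain. The change is worth making before analysis. It affects a secondary safety comparison and leaves the primary GSRS analysis as it is.

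**What to change.** 1. Reconcile Purpose and rationale (controls converted to azathioprine) with the Sample size calculation section (controls kept on MMF or EC-MPS). Patients converted to azathioprine have a conversion date; patients who stayed on MPA have none. Define an index date for each control so that a baseline eGFR exists.
2. Replace the ANOVA with ANCOVA of month-12 eGFR on group, with baseline eGFR as covariate, and report the adjusted difference with its 95% CI.
3. Report change from baseline beside it, and state that the two rest on different assumptions in non-randomised groups.
4. Limit the historical comparison to month 12 unless control eGFR is available at the other visits.
5. Label the comparison exploratory.

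The cost is short analysis text plus a small amount of chart work. Everolimus patients already have laboratory tests at visit 1. Controls must satisfy the eGFR exclusion, so screening them already calls for a baseline value once the index date is set. A reader might take this for a one-line edit, but the unresolved control definition makes it somewhat more than that.
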